#### Statistical considerations

1. Communities which drop out of the study will be omitted from analysis for all study period for which we have no data for that community. If a community rejoins at a particular phase, it will be included as before.
2. Evidence of poor model fit to the negative binomial regression will justify reporting additional models.
3. Permutation tests will be conducted with 10000 replications. If the critical value 0.05 lies within the Monte Carlo confidence interval for the P-value, we will replicate with 10,000,000 replications, and this will be reported.

#### Resistance comparison.

160 total communities from the mortality contingency study B (above) will be randomized to the 4 arms (blocked on baseline assignment, but not on rerandomization), and specimens collected from each of 36 children randomly selected from the census. The children will be selected from the age range 1-59 months (inclusive), at the 54 month census. The following outcomes are to be assessed:

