## 2 Design

Contingency study A. All communities in Niger will receive treatment at the conclusion of MORDOR Stage 1 (original study). Specifically, azithromycin communities will continue with azithromycin, and placebo communities will receive azithromycin at the 24 month visit (census number 5). Follow-up will occur at month 30 and month 36, providing one additional year of data.

Contingency study B. At the 36 month visit, rerandomization will occur, and half of communities will begin to receive placebo.

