#### Rectal Swab samples:

- 1) Outcome: Normalized read number for macrolide resistance determinants from DNA sequencing. These are to be physically pooled by community prior to sequencing; individual specimens will not be analyzed separately, and individual-level analysis will not be possible.

Analysis: We propose to use pairwise Wilcoxon rank-sum tests between each of the four treatment history groups, accounting for multiple comparisons as described [1-3]. All randomized communities will be included in the permutation testing.

This is the primary analysis for this study. All other analyses for the rectal swab collection (below) are secondary.

As a methodological sensitivity analysis, the Kruskal-Wallis (nonparametric one-way ANOVA), comparing all four arms. Such sensitivity analyses will be sharply distinguished from the primary prespecified analysis.

Mean fold difference between arms will be reported or plotted, as well.

- 2) Normalized read number of *Campylobacter* at the genus and species levels, derived from DNA sequencing. We will systematically compare the relative abundances of individual microbial taxa between groups at the species level by negative binomial Wald test using the Benjamini–Hochberg procedure for controlling FDR [4]. Differentially abundant taxa with a false discovery rate  $< 0.05$  and a twofold change will be considered as notable. Sensitivity test will be performed by first using the two-sided Kruskal–Wallis test at a predefined alpha of 0.05. Significantly different vectors resulting from the comparison of relative abundances between any two groups will be used as input for linear discriminant analysis (LDA), which produces an effect size [5]. The LDA will be set at 2 for all analyses.
- 3) Beta lactam resistance determinants will be analyzed, as in 1) above.
- 4) Other analyses will be conducted using the same pooling method, but will feature the use of Benjamini-Hochberg FDR procedures. The FDR is prespecified at 0.05.
  - a. Non-macrolide resistance determinants other than beta-lactam
  - b. Occurrence of different viruses or bacteria (we exclude eukaryotic organisms). Of particular importance are *Chlamydia* spp., malaria, and tuberculosis.
- 5) As in 1) above, but with the following outcome for each community: bacterial species normalized read counts. Statistically, we propose PERMANOVA comparison of all 4 arms, based on the  $L_2$  norm. As a sensitivity analysis, we will compare using the  $L_1$  norm.

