- 6) As in 4), but with species diversity as the primary outcome. We propose use of the  $L_2$  norm for the primary analysis, and then, as a sensitivity analysis, we will compare using the  $L_1$  norm, both expressed as effective number. The  $P$ -values will be derived from permutation.

Sample size. We chose  $N=160$  total communities, which provides approximately 80% power to detect a 3.5-fold difference in any pairwise comparison (assuming  $P=0.01$ , and an approximate SD of the base two logarithm of the read count (plus 1) of 2.25). The SD of the the log read count was derived from the placebo arm of the MORDOR 36 month data. The effect size (3.5 fold) is approximately half of what was observed in the MORDOR 36 month data.

NP Swab samples:

- 1) Analysis will compare macrolide resistance at the community level, using the Westfall-Young method [1] as above. This is the primary analysis for the NP swab study.
- 2) Exploratory analysis comparing the occurrence of different organisms at the genus and species levels. We prespecify an FDR of 0.05.

References

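### The 160-community resistance sample is balanced on the original arm but not on the rerandomised arm, so the power margin across the six primary comparisons is left to chance when equal groups could be drawn at no cost

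*SAP*

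**What the plan says.** SAP section 2 (Design) rerandomises the Niger communities at month 36, when "half of communities will begin to receive placebo". Crossing this with the original assignment gives four treatment histories.

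Under the heading Resistance comparison, the SAP takes 160 communities from contingency study B, with specimens collected at the 54-month census. The selection is "blocked on baseline assignment, but not on rerandomization". The four group sizes are not stated.

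Under Rectal Swab samples, item 1, the primary analysis is "pairwise Wilcoxon rank-sum tests between each of the four treatment history groups, accounting for multiple comparisons". That is six comparisons. The sample-size paragraph then claims "approximately 80% power to detect a 3.5-fold difference in any pairwise comparison", assuming P = 0.01 and "an approximate SD of the base two logarithm of the read count (plus 1) of 2.25".

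**The concern.** The four groups in the primary analysis are defined by two factors, and the sample is balanced on only one of them. The stated power leaves almost no reserve at 40 per group with the planned rank-sum test, yet nothing in the selection rule produces 40 per group. Some of the six comparisons will therefore have less power than stated, and which ones is decided by the draw.

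The six pairs are not equally exposed. Two groups from the same original arm always sum to 80, so one gains what the other loses. Two groups from different original arms can both be small. Four of the six pairs are of this second kind, including continuous azithromycin against original placebo now back on placebo, and different histories under the same current treatment.

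Only power is at stake. Unequal groups do not bias the comparison or disturb the type I error of a rank-sum or permutation test.

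**Working it through.** **Inputs.** From the SAP: 160 communities; a 3.5-fold difference; SD 2.25 on the log2(count + 1) scale; P = 0.01; half of communities rerandomised to placebo. Assumed: P = 0.01 is two-sided; log2 counts are normal with equal SD; blocking on the original arm means 80 communities from each; about 150 communities sit in each original-by-rerandomised cell. As a check, 156 per cell was also used, which is half of the 312 per arm in the SAP's mortality power statement.

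**Step 1: reproduce the stated figure at 40 v 40.**
- Effect: log2(3.5) = 1.807. Standardised: 1.807 / 2.25 = 0.803.
- z formula: 1.807 / (2.25 × √(2/40)) = 3.592. Less the critical value 2.576, this is 1.016, giving power 84.5%.
- Noncentral t without a rank-test penalty: 82.6%.
- Noncentral t with the Wilcoxon efficiency 3/π (effective n = 40 × 0.955 = 38.2 per group): noncentrality 3.510, power 80.4%.
- Direct simulation of the Wilcoxon test on normal data: 79.5%.
- One-sided 0.01 gives 88–90% and does not fit.

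The last two-sided formula suits the planned test and lies closest to the stated 80%. It is the main basis below, with the z formula as the generous end of the range.

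**Step 2: group sizes under the planned draw.** In each original arm, 80 communities are drawn from 150 + 150, so the number in one rerandomised group is hypergeometric with mean 40 and

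SD = √(80 × 0.25 × (300 − 80)/(300 − 1)) = √14.7 = 3.8.

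All four groups equal 40 in about 1% of draws. The two smallest groups average 35.7 and 38.2. The smallest is 36 or fewer in 59% of draws.

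**Step 3: power at particular splits.**

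| Split | t with 3/π | z |
|---|---|---|
| 40 v 40 | 80.4% | 84.5% |
| 35 v 45 (same original arm) | 79.6% | 83.9% |
| 35 v 35 (different original arms) | 73.4% | 78.4% |
| 31 v 31 (different original arms, extreme) | 66.4% | 72.1% |

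**Step 4: power over all draws (150 per cell).**

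| Quantity | t with 3/π | t alone | z |
|---|---|---|---|
| All groups at 40 | 80.4% | 82.6% | 84.5% |
| Given pair, average | 79.9% | 82.2% | 84.1% |
| Weakest of six, average | 76% | 78.5% | 81% |
| Weakest of six below 75% | about 31% of draws | 9% | 2% |

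On the main basis, the 5th percentile for the weakest pair is about 71%. The 2.5th percentile is about 78% for a same-arm pair and about 72% for a cross-arm pair. At least one pair falls below 80% in about 99% of draws, but the starting point there is only 80.4%; on the z formula the proportion is about 31%. Using 156 per cell gives nearly the same results. A simple binomial split is slightly worse, with the weakest pair averaging about 75%.

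**The case against.** The strongest reply is that the SAP's sentence is correct as written. Read per comparison, it says that whichever pair is named, power is about 80%, and the planned draw gives 79.9%. The weakest of six pairs, picked out after the split is known, is a quantity for which the SAP makes no claim, and a minimum must lie below the average whenever sizes vary. This stands. A reader might infer that the stated power is not delivered; the documents do not support that, because the average loss for a given pair is about 0.5 points (80.4 − 79.9).

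The size of the effect also depends on the formula, which the SAP does not give, and it is comparable with the uncertainty in the inputs. Raising the approximate SD from 2.25 to 2.35 lowers power at a perfect 40 v 40 to 76.1%, about the same drop. At a typical weakest pair of 36 v 38, the fold difference detectable with 80% power moves only from about 3.48 to 3.67. The SAP describes 3.5-fold as about half of what was seen at month 36; at about 7-fold, even 31 v 31 has about 98% power. All of this stands, and it makes the point minor.

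Finally, the scheme is openly disclosed, and the phrase about randomising communities to the four arms is ambiguous. If it already means 40 per group, only the parenthesis needs rewording. The documents also do not say when the 160 are selected. None of this gives a reason for leaving the second factor unbalanced.

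**Conclusion.** The point holds as a minor, avoidable inefficiency. The approximate 80% is fair for a pre-named pair before the draw, and the tests are valid. What the plan does not secure is that level for all six primary comparisons in the sample actually drawn. The weakest pair will typically have about 76% (5th percentile about 71%) on the formula suited to the planned test, or about 81% on the z formula, and it will usually be a pair from different original arms.

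This rests on a two-sided 0.01, normal log2 counts with equal SD, 80 communities per original arm, and about 150 communities per cell. The cell count is not in the documents, but 156 per cell changes little.

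**What to change.** Amend the selection rule under Resistance comparison to draw 40 communities at random from each of the four original-by-rerandomised cells, and state that the permutations follow the same scheme. Rerandomisation at month 36 precedes the month-54 collection, so both factors can be known when the sample is drawn. The cost is one line of SAP wording and one change in the sampling code, with no extra communities or swabs.

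If the sample has already been drawn, report the four realised cell sizes and the power for each of the six pairs at those sizes. If 40 per group was intended all along, reword the parenthesis to say so.

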#### Rectal Swab samples:

- 1) Outcome: Normalized read number for macrolide resistance determinants from DNA sequencing. These are to be physically pooled by community prior to sequencing; individual specimens will not be analyzed separately, and individual-level analysis will not be possible.

Analysis: We propose to use pairwise Wilcoxon rank-sum tests between each of the four treatment history groups, accounting for multiple comparisons as described [1-3]. All randomized communities will be included in the permutation testing.

This is the primary analysis for this study. All other analyses for the rectal swab collection (below) are secondary.

As a methodological sensitivity analysis, the Kruskal-Wallis (nonparametric one-way ANOVA), comparing all four arms. Such sensitivity analyses will be sharply distinguished from the primary prespecified analysis.

Mean fold difference between arms will be reported or plotted, as well.

- 2) Normalized read number of *Campylobacter* at the genus and species levels, derived from DNA sequencing. We will systematically compare the relative abundances of individual microbial taxa between groups at the species level by negative binomial Wald test using the Benjamini–Hochberg procedure for controlling FDR [4]. Differentially abundant taxa with a false discovery rate  $< 0.05$  and a twofold change will be considered as notable. Sensitivity test will be performed by first using the two-sided Kruskal–Wallis test at a predefined alpha of 0.05. Significantly different vectors resulting from the comparison of relative abundances between any two groups will be used as input for linear discriminant analysis (LDA), which produces an effect size [5]. The LDA will be set at 2 for all analyses.
- 3) Beta lactam resistance determinants will be analyzed, as in 1) above.
- 4) Other analyses will be conducted using the same pooling method, but will feature the use of Benjamini-Hochberg FDR procedures. The FDR is prespecified at 0.05.
  - a. Non-macrolide resistance determinants other than beta-lactam
  - b. Occurrence of different viruses or bacteria (we exclude eukaryotic organisms). Of particular importance are *Chlamydia* spp., malaria, and tuberculosis.
- 5) As in 1) above, but with the following outcome for each community: bacterial species normalized read counts. Statistically, we propose PERMANOVA comparison of all 4 arms, based on the  $L_2$  norm. As a sensitivity analysis, we will compare using the  $L_1$  norm.
- 6) As in 4), but with species diversity as the primary outcome. We propose use of the  $L_2$  norm for the primary analysis, and then, as a sensitivity analysis, we will compare using the  $L_1$  norm, both expressed as effective number. The  $P$ -values will be derived from permutation.

Sample size. We chose  $N=160$  total communities, which provides approximately 80% power to detect a 3.5-fold difference in any pairwise comparison (assuming  $P=0.01$ , and an approximate SD of the base two logarithm of the read count (plus 1) of 2.25). The SD of the the log read count was derived from the placebo arm of the MORDOR 36 month data. The effect size (3.5 fold) is approximately half of what was observed in the MORDOR 36 month data.

NP Swab samples:

- 1) Analysis will compare macrolide resistance at the community level, using the Westfall-Young method [1] as above. This is the primary analysis for the NP swab study.
- 2) Exploratory analysis comparing the occurrence of different organisms at the genus and species levels. We prespecify an FDR of 0.05.

References

